This protocol is to examine the effectiveness of the pragmatic implementation of SHARING CHOICES in primary care practices (Aims 3 and 4 of the overall grant). The goal of SHARING CHOICES is to proactively engage family in ongoing interactions with primary care and stimulate and support ACP and attention to ADRD in all primary care patients and particularly for those with ADRD, throughout the disease trajectory. The design is a cluster randomized trial with pragmatic implementation of SHARING CHOICES into routine clinical care to examine the effectiveness for all older patients and persons with ADRD diagnoses. The components of SHARING CHOICES, which are all available in routine primary clinical care but have not been systematically implemented, include: 1) an electronic message or letter from the primary care practice introducing the components of SHARING CHOICES available to patients in their practices, including ACP, 2) a person-family agenda-setting checklist to align patient and family perspectives regarding the role of the family member in primary care interactions, 3) ongoing access to a trained and certified ACP facilitator to lead ACP conversations with patient and family, in collaboration with the patient's primary care clinician, 4) facilitated registration for the patient portal (including family) to enable and extend electronic interactions and information access to family members, when this is consistent with patient preferences, and 5) implementation support, education and resources about ADRD for practice staff, tailored to SHARING CHOICES practices. This work is informed by the outcomes of stakeholder and patient interviews and focus groups and a pilot study in which we refined SHARING CHOICES to optimize implementation for primary care patients aged 65 and over and their families, including patients with ADRD.

Study Title

Pragmatic Trial: Improving Communication for Primary Care Patients

Objectives

This study is a pragmatic trial to evaluate the effectiveness of SHARING CHOICES included in routine clinical care with primary care patients age 65 years and over

including those with mild to severe ADRD. We will evaluate uptake of the SHARING CHOICES components by patients and family and study outcomes through secondary analysis of information collected in routine clinical care.

Design and Outcomes

This will be a pragmatic randomized, controlled trial of SHARING CHOICES included in routine clinical care in primary care practices. Randomization will be at the practice level. All components of SHARING CHOICES are currently available in primary care but have not been routinized in these practices. Sites randomized to control will continue with usual care, while sites randomized to SHARING CHOICES will have the SHARING CHOICES components included in routine clinical care, including outreach on the components and availability of certified ACP facilitators. Facilitator staff will participate in two fidelity simulations with standardized patients (SPs). Facilitators will be assessed according to a pre-designed checklist developed to determine fidelity of ACP conversations occurring as part of the pragmatic trial. Results of the fidelity assessment will be used to evaluate the effectiveness of ACP training protocols central to the implementation of SHARING Choices in usual care. Simulation activities for this trial will pose minimal risk to facilitators, offer opportunities for debriefing with expert faculty to support management and emotional response to encounters including just-in-time coaching to reinforce exemplary skills.

The study outcomes will be collected through secondary analysis of data collected for non-research purposes. Primary outcomes will be extracted from the electronic health record (EHR) and Maryland-District of Columbia health information exchange (CRISP) and analyzed at the practice level, including rates of advanced care planning documentation, advance directive documentation and potentially burdensome care within 6 months of death for patients who have died. Data extracted by CRISP and delivered to the study team will only be for patients who died during the observation time period during the trial. Death data will be collected from the Vital Statistics Agency by CRISP.

Trial Procedures and Duration

The control group will receive usual care, comprising standard primary care at participating practices. Patients at implementation practices will receive usual care in addition to SHARING CHOICES components. The SHARING CHOICES components include: 1) an invitation letter from the primary care practice introducing SHARING CHOICES initiatives, 2) access to a facilitator trained in the protocol and leading ACP for persons age 65 and older including those with a diagnosis of ADRD and family members who are interested in engaging, 3) a person-family agenda-setting checklist to align perspectives about the role of family and stimulate discussion about health care issues and ACP, 4) facilitated registration for the electronic health record portal to enable and extend electronic interactions and information access to patients and family, and 5) implementation support, education and resources about ADRD for practice staff.

Patients and families at SHARING CHOICES practices interested in ACP will have

access to a practice ACP facilitator to schedule a discussion. SHARING CHOICES will be available to all patients 65 or older in these practices. Trained and certified ACP facilitators will lead ACP. All facilitators will be trained in all elements of the SHARING CHOICES protocol, with supplemental training for ADRD.

ACP discussions will include an initial meeting of up to 45 minutes, with a process for scheduling future contacts as needed. We expect meetings will most often occur at the primary care practice, but may also occur by phone or through telehealth, in the community or at the individual or family residence. In the initial meeting the facilitator will follow a conversation guide and employ motivational interviewing techniques to evaluate readiness and facilitate uptake and adoption of SHARING CHOICES components. Patients will be offered all components, with the duration and nature of the conversations and resulting decisions tailored to individual preferences.

To evaluate ACP facilitator implementation skill and competency to perform ACP conversations, each facilitator will do two case-based simulations with standardized patients (SPs) via teleconference (**D2, D3**). The first case is an SP with mild cognitive impairment and the second case involves an SP with dementia and their caregiver. Each simulation will include a 10-minute pre-brief session (**D1**) to orient the facilitator to the simulation and a 30-minute simulation with the SPs followed by a 15-minute debrief to identify adherence to the intervention, quality of delivery, and areas for further improvement. Adherence will be measured using the Advance Care Planning (ACP) Facilitator Evaluation Checklist, a short fidelity instrument adapted from SHARE (IRB00242431) and Respecting Choices® to evaluate communication skills and the key elements in an ACP conversation (**E1, E2**). The results will also be used to inform additional booster training for facilitator staff.

The overall duration of patient follow-up will be 12 months as measured from the most recent primary care appointment date when the patient is sent the SHARING CHOICES materials. The overall study duration is expected to be 18 months.

Sample Size and Population

We will engage a diverse mix of practices by geographic region (urban, suburban, rural) and size. The unit of randomization for this study is the primary care practice. Study participants will include all primary care patients age 65 and over, including those with ADRD and their family at up to 100 primary care practices. We anticipate that 9,200 of 87,000 of older patients will have a diagnosis of ADRD, and 7,000 will die within 12 months of study entry and be eligible for the potentially burdensome end-of-life care outcomes.

STUDY TEAM ROSTER

Principal Investigator: **[name]**

[name]
[name]
[contact]
[contact]

Medstar Site Principal Investigator: [name]

MedStar Institute for Quality and Safety
[name]
[name]
[name]
[contact]
[contact]

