1.1 Primary Objective

This study (Aims 3 and 4 of the overall grant) aims to evaluate the implementation effectiveness of SHARING CHOICES in primary care practices. Effectiveness will be evaluated in a pragmatic, cluster randomized trial of primary care practices to examine the impact of SHARING CHOICES on the rates of ACP, AD documentation, and end of life outcomes in patients aged 65 years and older, including those with mild to severe ADRD.

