
3 **STUDY DESIGN**

This study will evaluate the implementation effectiveness of SHARING CHOICES to increase the rate of advance directive documentation and improve end-of-life outcomes using a pragmatic, cluster randomized trial design. Outcomes from data collected in routine clinical care will be aggregated at the practice level in up to 100 diverse primary care practices from 2 health systems. Practices randomized to SHARING CHOICES will have information electronically sent or mailed to their patients. SHARING CHOICES practices will have access to a trained ACP facilitator who will be available to engage the patients and their healthcare agent in ACP discussions when desired. We will evaluate effectiveness of SHARING CHOICES by analyzing data collected for non-research purposes from the electronic health record (EHR). To facilitate understanding of how to operationalize the primary endpoint of advance directive documentation and with support from JHCP and MedStar Health leadership, we will perform an advance directive audit within the EHR to characterize the quality of data existing in the electronic health record across 19 JHCP and 35 MedStar clinics prior to the launch of the intervention. To ensure ACP facilitator implementation fidelity to the methodological training components of the ACP conversation, facilitation staff will be evaluated via supervised interactions with simulated patients (**D1, D2, D3**).

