6 STUDY PROCEDURES

Audit

Preparatory to the detailed audit, an exploratory analysis will be performed using Natural Language Processing (NLP) to determine the number of existing patient records with a textual reference to advance care planning processes and documentation. This analysis will not include patient identifiers. NLP will be used to identify the proportion of patients whose charts do and do not have official documentation of an advance directive (e.g., documentation of a named health care agent or completion of a living will) and/or MOLST/MOST who also have a textual reference to advance care planning-related conversations or documentation in the clinicians' note. Results will be examined in the aggregate by clinic site. We seek to understand the percentage of patients at each clinic who have engaged in an ACP-related encounter by whether they do or do not have documentation of their wishes.

For each of the 19 JHCP and 35 MedStar Health clinics that are part of this trial, we will randomly select 30 - 40 electronic health records of patients age 65 and older under the care of a clinician at the clinic for whom an advance directive has been documented in the electronic health record. Trained study staff at JHCP and MedStar Health will manually review the documented advance directive to confirm that the uploaded document is an advance directive, and, if so, whether the advance directive includes the naming of a health care agent only, the completion of a living will only, or both. The goal of the advance directive audit will be to identify the percentage of advance directives that are documented as being completed that are in fact an advance directive. We will additionally identify variability in the accuracy of advance directive completion by clinic, by patient age group, and for patients with and without a diagnosis of dementia.

Mailings

PHI from EPIC will be requested and disclosed to School of Public Health team members to access data on patients who may be eligible for the advance care planning services – this data will include name, age, primary care physician, upcoming appointments, and address. The team members will use this to identify patients who can receive the SHARING CHOICES intervention (over 65 and with an upcoming appointment in primary care clinics randomized to SHARING CHOICES) and will use patient names and addresses in order to mail the information about the SHARING CHOICES components available in their clinic.

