Outcomes from practices randomized to SHARING CHOICES will be compared to practices within the same system who are randomized to usual care. Outcomes will be assessed at the level of the practice. Control practices will continue to deliver their usual care practices with respect to ACP and agenda setting.

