9.2 Sample Size and Randomization

The unit of randomization for this study is the primary care practice. Practices will be stratified by health system and balanced on practice characteristics, including practice size, geographic location (urban, rural, suburban), and patient mix by race.

Practices randomized to control will continue to provide usual care. Practices randomized to SHARING CHOICES will provide usual care as well as the components of SHARING CHOICES. SHARING CHOICES will be available to all patients ages 65 and older who receive care at up to 33 practice sites.

9.3 Interim analyses and Stopping Rules: N/A.

9.4 Outcomes will include the rates of advance directive documents uploaded to the EHR (primary outcome), advance care planning documentation, and potentially burdensome care within the last six months of life.

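### The 12-month follow-up clock starts at an event that occurs only in intervention practices, so control and unmailed patients have no time zero and the primary outcome has no window

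*Combined protocol and SAP*

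**What the plan says.** The summary fixes a follow-up length of 12 months, "as measured from the most recent primary care appointment date when the patient is sent the SHARING CHOICES materials", within an expected study duration of 18 months. This is the only start point for follow-up that the protocol defines.

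The materials belong to the intervention. Section 3 states: "Practices randomized to SHARING CHOICES will have information electronically sent or mailed to their patients". The Mailings part of Section 6 describes the patients selected as "over 65 and with an upcoming appointment in primary care clinics randomized to SHARING CHOICES". Control practices continue with usual care.

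The population and the comparison are broader. Under Sample Size and Population the summary states: "Study participants will include all primary care patients age 65 and over". Section 1.1 seeks the effect "on the rates of ACP, AD documentation, and end of life outcomes in patients aged 65 years and older". The Outcomes part of Section 6 states: "Outcomes from practices randomized to SHARING CHOICES will be compared to practices within the same system who are randomized to usual care".

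Section 9.4 names the primary outcome only as "rates of advance directive documents uploaded to the EHR (primary outcome"). It gives no start, end or cohort date. Directives exist before launch, because the audit in Section 6 samples records of patients "for whom an advance directive has been documented in the electronic health record". No rule says how such patients count.

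Two other time references appear in the summary, *study entry* (for the anticipated deaths) and the *observation time period* (for the decedent data). Neither is defined. Section 10.2.1 lists directive status without a date, lists mailing dates for intervention clinics only, and removes patients found in both health systems without saying which practice keeps them.

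**The concern.** Randomisation by practice protects the comparison only if both arms use the same time zero, the same window and the same denominator. Here the one defined start date arises after randomisation, because the intervention was delivered, and it cannot exist in a control practice. The control window is then left to whoever runs the analysis. So is the choice of keeping unmailed intervention patients in the denominator with no countable follow-up, or leaving them out. Each choice can move the primary result with no treatment effect, and adding practices does not remove the problem.

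**Working it through.** The plan has no power or sample-size calculation to reproduce. The check sets the sections side by side and adds small calculations for scale.

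**1. Who has a time zero under the summary's rule**

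| Group | In stated population | Sent materials | Time zero |
|---|---|---|---|
| Intervention, mailed | yes | yes | appointment linked to the mailing |
| Intervention, not mailed | yes | no | none |
| Control | yes | no | none |

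**2. Whether another section fills the gap.** Section 9.1 is marked not applicable. Section 9.4 gives no window for the primary outcome and Section 9.5 adds none. Section 10.2.1 names no index date for control patients.

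**3. Calendar.** 18 − 12 = 6 months is the longest period over which index appointments can fall if everyone is to complete 12 months. Section 10.2.1 allows for more than one mailing. If the *most recent* appointment moves with a later mailing, an index after month 6 cannot complete 12 months within the study.

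**4. Unequal windows, pure illustration.** Assume a 12-month upload probability p in both arms, a constant hazard and no effect. Count one arm over 12 months and the other over 18. The 18-month probability is 1 − (1 − p)^(18/12).

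| Assumed p | 18 months | Gap (points) | Ratio | Ratio, arms swapped |
|---|---|---|---|---|
| 5% | 7.4% | 2.4 | 1.48 | 0.68 |
| 10% | 14.6% | 4.6 | 1.46 | 0.68 |
| 20% | 28.4% | 8.4 | 1.42 | 0.70 |

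The sign depends entirely on which arm gets the longer window. The denominator also works both ways. Keeping unmailed patients with no countable follow-up lowers the intervention rate. Dropping them restricts that arm to patients with appointments, who may have more opportunity to file a directive.

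**5. Decedents.** The summary anticipates 7,000 deaths among 87,000 patients within 12 months of study entry: 7,000/87,000 = 8.05%. At a constant hazard (assumed), the 18-month proportion is 1 − (1 − 0.0805)^1.5 = 11.8%, about 10,290 deaths. The undefined observation period could therefore change the number of qualifying decedents by about 3,290. The six-month burdensome-care window is counted back from death and is not itself affected.

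**6. Directives already on file.** Let b be the share with one at launch. Assume 5% new uploads among the rest in control and a true ratio of 1.5. If any directive on file at the end counts, the ratio is (b + 0.075(1 − b)) / (b + 0.05(1 − b)):

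- b = 0.1: 0.1675/0.145 = 1.16
- b = 0.2: 0.26/0.24 = 1.08
- b = 0.4: 0.445/0.43 = 1.03

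The absolute difference is 0.025(1 − b), or 2.25, 2.0 and 1.5 points. Counting only new uploads among all patients gives the same difference. The dilution therefore applies to ratio measures only.

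**The case against.** The strongest defence is that the clock sits in a summary paragraph on duration and that neither Section 9.4 nor 9.5 invokes it. Outcomes are aggregated by practice, and a practice-level rate may need no patient-level start date. Twelve months may be the intended outcome window, and a qualifying visit applied to both arms would be a natural reading. Section 3 says the pre-launch audit is meant to help make the primary endpoint operational, so the definition is openly still in progress. The appointment condition appears only under Mailings in Section 6; Section 5 describes an electronic notice without it. The variable list in Section 10.2.1 is illustrative, so upload dates may well be extracted. An uploaded document can also be read as a new event, not a status on file.

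Much of this stands, and it limits the point. It does not close the gap. A practice-level rate still needs a dated numerator and denominator, and neither is written. The audit concerns whether filed documents are genuine directives; it supplies no index date or window.

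A reader might go further and infer that the rule biases the trial toward hiding a real effect. The documents do not support that. A direction appears only once a control window is paired with the intervention clock, and the protocol describes no such pairing. Nor do they support the inference that only mailed patients will be analysed, since the stated population is everyone aged 65 or older.

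**Conclusion.** The point holds and should be settled before outcome data are seen, because it concerns the definition of the primary outcome. It is more than missing detail: the one rule that is written gives an index in one arm only, and that index depends on the intervention, so it cannot yield a like-for-like comparison. This conclusion rests on the text alone.

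The direction and size of any bias cannot be derived from the documents. The unequal-window and on-file figures use assumed rates and show only that the choice matters. The decedent figure uses the protocol's own counts with an assumed constant hazard. Practice attribution, duplicate patients and undated directive status are lesser parts of the same gap; the documents do not give the number of duplicates.

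**What to change.** Replace the summary's clock with one index date and one 12-month window, defined identically in both arms and independent of mailing. Either of two rules would serve:

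- a practice launch date, assigned to every practice in both arms at randomisation if roll-out is staggered; or
- the first qualifying visit after launch, identified in the same way in both arms.

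In Section 9.4, define the primary outcome as new directive uploads in that window among all patients aged 65 or older attributed to the randomised practice. State one rule for both arms on directives already on file. Settle it with the audit results, since the accuracy of that record field is not yet known, and before outcomes are seen. Use the same index to define study entry and the observation period. In Section 10.2.1, state which practice keeps a patient found in both systems, extract upload dates for both arms, and use mailing dates only to describe uptake.

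The cost is wording in three places, an attribution rule, index dates for all practices or patients, and upload dates, all from routine records. No new patients or procedures are needed. Twelve months fits within 18 if the index falls in the first 6.

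Each rule has a downside. With a launch date, patients mailed late or never dilute the effect, and a closed list omits those who join later. A visit-based index omits patients who do not attend, and it is symmetric under no effect only if attendance does not differ by arm. Excluding patients with a directive on file would reduce the analysed number by a share that the documents do not give.

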1.1 Primary Objective

This study (Aims 3 and 4 of the overall grant) aims to evaluate the implementation effectiveness of SHARING CHOICES in primary care practices. Effectiveness will be evaluated in a pragmatic, cluster randomized trial of primary care practices to examine the impact of SHARING CHOICES on the rates of ACP, AD documentation, and end of life outcomes in patients aged 65 years and older, including those with mild to severe ADRD.

2 BACKGROUND AND RATIONALE

2.1 Background on Condition, Disease, or Other Primary Study Focus

Engaging family in primary care is particularly important in ADRD because of the important role assumed in medical decision-making,(18-21) especially at the end of life.(22-24) Our study seeks to improve communication for persons with ADRD by establishing a structured protocol to proactively engage family in ongoing interactions with primary care and stimulate and support ACP and attention to ADRD in primary care throughout the disease trajectory. Our premise is that individuals and families expect primary care practices to initiate ACP(25) and provide information and referrals for ADRD needs, (26, 27) but that individual, family, and system factors including time, knowledge, and resources inhibit these conversations from occurring.(12) This protocol aims to inform decision-making regarding routine implementation of SHARING CHOICES, which seeks to better equip patients and family with the knowledge, skills, and support to engage in more effective communication and ACP.

